Background, Significance and Rationale

Background, Significance and Rationale

Previous research has suggested that the endocannabinoid system may serve a regulatory function in frontal-striatal brain circuits which have been implicated in anxiety disorders and Obsessive Compulsive Disorder (OCD) (Lutz et al. 2015, Gremel et al. 2016). In addition, there is an emerging body of evidence which demonstrates a potential role for drugs that target cannabinoid receptors in the treatment of anxiety disorders and Tourette's syndrome (Curtis et al. 2009, Müller-Vahl et al. 2013, Blessing et al. 2015). Data from animal studies (Deiana et al. 2011, Nardo et al. 2013, Breuer et al. 2016) suggest a potential benefit to these compounds in OCD as well. However, to date studies in humans are limited to case reports (Schindler et al. 2008). The purpose of this double-blind, placebo-controlled, within-subject study is to examine the effects of different cannabinoids, delivered in a laboratory setting, on adults with primary OCD. In order to accomplish this, adults with OCD who are also occasional marijuana smokers will be recruited for 3 outpatient laboratory sessions over the course of 2-3 weeks. In the laboratory, patients will receive different combinations of the cannabinoids tetrahydrocannabinol (THC, the active ingredient in the marijuana plant) and cannabidiol (CBD, a cannabinoid constituent of marijuana which has demonstrated therapeutic potential across a variety of psychiatric disorders including depression, anxiety, and psychosis [Campos et al. 2012]) or placebo. We will then measure whether or not patients respond to these agents (i.e. experience a significant reduction in their OCD symptoms) in the acute setting.

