The need to understand the impact of smoked THC and CBD in clinical populations is supported by 3 prior studies by Valerie Curran’s group at University College London. In a 2008 study, hair samples collected from a population of 140 users of a variety of illicit substances were screened for THC and CBD. Subjects who screened positive for THC alone showed higher levels of positive schizophrenia-like symptoms compared to both those who screened negative for cannabinoids and those who screened positive for THC and CBD, suggesting that smoked CBD may have antipsychotic properties. A second study in 2010 in which subjects were assessed after using their chosen strain of cannabis indicated that smokers of high CBD:THC strains showed a decreased attentional bias towards drug and food stimuli and less self-reported liking of cannabis stimuli. These data suggest that CBD may mitigate the effects of THC and may have utility as a treatment for cannabis dependence. Finally, in a 2014 study of 48 cannabis-using subjects who received inhaled THC, CBD, THC+CBD, and placebo, subjects showed improved recognition of facial affect without any effect on feelings of being “stoned” after receiving CBD alone. In contrast, THC produced a reduction in facial affect recognition, while THC+CBD and placebo showed no effect. Both THC alone and THC+CBD in combination increased feelings of being “stoned” relative to placebo. The results of this laboratory study provide early evidence that agents that target the endocannabinoid system may produce contrasting neurocognitive effects. In total, the findings from these studies suggest that further study of the impact of THC and CBD in psychiatrically ill populations (including OCD) is warranted.

Specific Aims and Hypotheses

Specific Aims and Hypotheses

Specific Aims:

To compare the effects of High THC (5-10%)/Low CBD (<1%) marijuana, Low THC (<1%)/High CBD (>10%) marijuana, and placebo (0% THC and CBD) marijuana in adults with primary OCD who also occasionally smoke marijuana.

Specific Hypothesis:

In the acute setting, smoked marijuana in both high THC/low CBD and low THC/high CBD concentrations will lead to a reduction in symptoms in adults with primary OCD who are also occasional marijuana smokers as compared to placebo.

Description of Subject Population

Sample #1

Specify subject population

Adults who meet DSM 5 criteria for OCD who are also occasional marijuana smokers

Number of completers required to accomplish study aims

15

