
Projected number of subjects who will be enrolled to obtain required number of completers

20

Age range of subject population

21 - 55

Gender, Racial and Ethnic Breakdown

Based on the community from which we will be drawing patients and proportions to those encountered during previous clinical trials at this site, we expect the sample to be approximately 5 percent Hispanic and 95 percent Non-Hispanic. Racially, we expect there will be 89 percent White, 9 percent Black, 2 percent Asian. Based upon the prevalence of OCD, it is expected that the sample will be approximately 1 to 1 = male to female.

Description of subject population

The sample will consist of a maximum of 15 female and male adults with a diagnosis of OCD and clinically significant symptoms (i.e., a Y-BOCS score of at least 16) who are also occasional marijuana smokers. Subjects may or may not be seeking treatment for their OCD but will not be seeking treatment for their marijuana use. ~~Minorities and females will be well represented in this study.~~

Recruitment Procedures

Describe settings where recruitment will occur

Recruitment will draw from the broadest possible population with respect to gender and ethnic origin. IRB-approved radio/internet/newspaper advertisements and flyers will be used to recruit subjects (materials to be submitted).

We will also use various internet sites (e.g., Twitter, Google advertising, Craigslist, Facebook, LinkedIn, Research Match, Bangitout.com, Clinicaltrials.gov, twitter, Psychology Today, Craigslist, and other similar sites) as additional recruitment tools.

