protocol with the volunteer and document their consent to the research study. The physician and volunteer will then sign the study consent form.

4) Study procedures will begin after the study physician verifies that the participant meets inclusion/exclusion criteria, understands the medical risks of participation, and is capable of providing informed consent. [name], the senior study physician, will settle any disagreements among the study team as to a volunteer's eligibility, and will make the final decision as to study participation. Behavioral observations and testing will be carried out by one of the study clinicians. In the event of an emergency, one of the study physicians will be available by phone. [name] and other psychologists, nurses, and physicians are around the corner or down a corridor from the outpatient laboratory. We do not test research participants unless we are sure that a physician is available by telephone or by pager in the event of an emergency. A set of emergency procedures, including a list of physicians, telephone and pager numbers is posted in the outpatient laboratory.

Medication: Patients will be administered smoked marijuana at one of the following concentrations: High THC (5-10%)/Low CBD (<1%), Low THC (<1%)/High CBD (>10%), or placebo (0% THC and CBD). The order in which they receive each concentration will be randomized. Participants will complete 1 or 2 sessions per week depending on timing and subject availability. Because of cannabidiol's long terminal half-life (21-33 hours), we are allowing time for drug clearance in between sessions (at least 3 days) to avoid potential carryover effects (Consroe et al., 1991).

General Design: There will be three 4-hour laboratory sessions, which will occur between 0900 and 1300 hr, testing the effect of smoked marijuana on OCD symptoms. Sessions will occur once or twice per week over a period of approximately 3 weeks depending on each participant's availability.

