Laboratory Sessions: Participants will be instructed that they should not smoke either marijuana or cigarettes on the morning of a session (beginning at midnight). We will do a carbon monoxide (CO) test upon their arrival in the laboratory to verify nothing was recently smoked. Participants will also be given a breathalyzer test to ensure that they did not drink alcohol prior to arrival. At each visit, urine samples will be tested for drug use, and, for women of child-bearing age, for pregnancy. Subjects who are found to be pregnant will be discontinued from the study, but will receive payment for those procedures that they have already completed. Participants with high COs or those testing positive for drugs other than marijuana will be re-scheduled and possibly excluded from further participation. Patients will then receive either high THC (5-10%)/low CBD (<1%) marijuana, low THC (<1%)/high CBD (>10%) marijuana, or placebo (0% THC and CBD). The marijuana used in the study will be provided by the NIDA. We will guide participants through smoking individual puffs of marijuana using cue-dosing procedures until 50% of the cigarette has been smoked. Specifically, for each puff, participants will be instructed to inhale for 5 seconds and hold each puff in the lungs for 10 seconds. There will be approximately a 40-second interval between each puff. For the first hour after marijuana administration, clinical ratings, scales, and BP/HR will be obtained every 20 minutes. During the second hour, these measures will be repeated once every half-hour, and then again at the conclusion of the third hour (see Table 1). The session will end after the third hour. Participants will be allowed to leave the facility when they pass the field sobriety test, and will be instructed not to drive a car or use other drugs or alcohol for at least 8 hours after marijuana administration.

Table 1. Session Schedule

| TIME (min) | EVENT |
|------------|--|
| -50 | CO, collect urine, breathalyzer, start breakfast |
| -30 | Finish breakfast (set timer for 30 min), balance, TLFB, BP/HR, VAS, YBOCCS, STAI |
| 0 | Marijuana administration |
| 20 | BP/HR, VAS, YBOCCS, MRF, STAI |
| 40 | BP/HR, VAS, YBOCCS, MRF, STAI |
| 60 | BP/HR, VAS, YBOCCS, MRF, STAI |
| 90 | BP/HR, VAS, YBOCCS, MRF, STAI |
| 120 | BP/HR, VAS, YBOCCS, MRF, STAI |
| 180 | BP/HR, VAS, YBOCCS, MRF, STAI, Field Sobriety Test, participant discharge |

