Cannabis Effects: We will use a random-effects linear mixed model to evaluate changes in each continuous outcome (YBOCCS, OCD-VAS, STAI-S MRF, cardiovascular measures) as a function of condition (THC, CBD, placebo), time point, and their interaction. Mixed-effects modeling accounts for clustering of repeated measures within subjects, allows time to be modeled as a continuous rather than categorically, and has been used in similar acute pharmacological challenge studies (Rodriguez et al. 2013). The model will include participants as a random effect, condition and time as fixed within-subjects factors, the interaction between condition and time, and a random intercept. Given that the interval between sessions increases over the course of each session, we will model time as a continuous variable. We will use contrasts within each mixed-effects linear regression model to estimate differences in outcomes between both active cannabis varieties and placebo at different time points. All statistical tests will be conducted using an alpha level of 0.05, two-tailed.

Other Effects: Though we have no a priori hypotheses about the effects of age, gender, comorbid diagnoses (e.g. MDD), or other factors that might influence our participants' response to cannabis, we will nonetheless explore the possibility of such effects by including these factors as covariates in separate analyses.

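### The active-placebo contrasts do not adjust for each session's own pre-dose score, which is already collected; this costs precision, and the adjustment needs a session random effect beside it

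*Combined protocol and SAP*

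**What the plan says.** The design is described as follows: "The purpose of this double-blind, placebo-controlled, within-subject study". Each participant has three sessions, in randomized order and at least 3 days apart (Study Procedures, Medication).

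In Table 1 the row for 30 minutes before dosing reads "Finish breakfast (set timer for 30 min), balance, TLFB, BP/HR, VAS, YBOCCS, STAI". The same measures plus the MRF follow at 20, 40, 60, 90, 120 and 180 minutes. The last row reads "BP/HR, VAS, YBOCCS, MRF, STAI, Field Sobriety Test, participant discharge". Every listed outcome except the MRF therefore has a pre-dose value in each session.

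The Cannabis Effects paragraph of the Data Analytic Plan fits a linear mixed model to each outcome, with a random intercept for participant and fixed condition, time and condition-by-time. Contrasts within the model are used "to estimate differences in outcomes between both active cannabis varieties and placebo at different time points". The paragraph says that changes will be evaluated, but it does not define change and does not mention the -30 minute reading. The Other Effects paragraph names age, gender and comorbidity as exploratory covariates, not the pre-dose score. The shorter repeated-measures ANOVA statement under Study Procedures has no pre-dose adjustment either.

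**The concern.** A participant intercept removes differences between people. It does not remove differences between one person's days. If a participant is more symptomatic on the placebo day than on the THC day, that gap goes into the drug-placebo difference.

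Day effects are plausible here. Sessions spread over about 3 weeks, marijuana use of up to once a day is allowed at entry, and abstinence is required only from midnight before a session. The hypothesis is an acute reduction in symptoms, which itself suggests the same morning's pre-dose state as the reference.

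With 15 completers there is little room for avoidable error variance, and the reading that would remove part of it is already scheduled.

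**Working it through.** **The plan's own figure.** "Number of completers required to accomplish study aims" is 15 and enrolment is 20, which implies 15/20 = 75% completion. No effect size, SD, correlation or power accompanies these numbers, so 15 cannot be re-derived. It is used below as the number with all three sessions.

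**Assumptions (not in the documents).** Total variance is 1 and participant share 0.5. Session share is s and residual share 0.5 - s. Variances are equal before and after dosing, and no session is missing.

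**Unadjusted contrast, mean of six post-dose readings.** The within-person variance of a session mean is V = s + (0.5 - s)/6. The SE of active minus placebo is sqrt(2V/15).

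**Adjusted contrast.** The pre-dose reading has within-person variance 0.5 and covariance s with the session mean, so adjustment removes s²/0.5. A session-level analysis has 45 - 15 - 2 = 28 residual degrees of freedom before the covariate. Estimating the slope costs a factor of about 1 + 1/26. The SE is sqrt(2(V - s²/0.5)(27/26)/15).

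| s | V | SE unadjusted | V - s²/0.5 | SE adjusted | Change in SE |
|---|---|---|---|---|---|
| 0 | 0.0833 | 0.105 | 0.0833 | 0.107 | +2% |
| 0.1 | 0.1667 | 0.149 | 0.1467 | 0.142 | -4% |
| 0.2 | 0.2500 | 0.183 | 0.1700 | 0.153 | -16% |
| 0.3 | 0.3333 | 0.211 | 0.1533 | 0.146 | -31% |

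Simulation of the same session-level analysis gives SEs of 0.105/0.107, 0.148/0.141, 0.181/0.152 and 0.209/0.145, with type I error near 5%.

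**How much of the day effect goes.** The share of session variance removed is (s²/0.5)/s = s/0.5, or 20%, 40% and 60% at s = 0.1, 0.2 and 0.3. One noisy reading does part of the job.

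**Other uses of the -30 minute reading.**
- Change scores: the variance becomes V + 0.5 - 2s, which is 0.467, 0.350 and 0.233 at s = 0.1, 0.2 and 0.3. The unadjusted values are 0.167, 0.250 and 0.333. Change scores beat no adjustment only when s exceeds 0.25, that is, when the within-person correlation between single pre- and post-dose readings exceeds 0.5.
- As a seventh response under the participant-only intercept: with within-person variance scaled to 1 and half of it between sessions, the simulated SD of the 60-minute contrast is 0.282. It is 0.288 with post-dose data only and 0.221 with covariate adjustment.

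**Do the tests become valid?** The planned model treats the six readings in a session as independent given the participant. In the last setting its mean reported SE is 0.150 against a true SD of 0.288, and type I error is about 31%. Adding the pre-dose covariates alone does not cure this. Back on the scale of the table, type I error of the 60-minute contrast after adjustment, without a session term, is about 14% at s = 0.1 and 20% at s = 0.2. Another set of runs gave 16 to 17% across those shares. With the session term it is about 4 to 6%.

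**Slopes.** A shift that is constant within a session adds the same amount to all six readings and cancels from the within-session slope. The condition-by-time estimates do not carry the day effect.

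**The case against.** The plan never says that raw scores are compared. Because it speaks of changes, a sponsor could say that the -30 minute value enters as a response or through change scores. That stands as a matter of wording: the plan is unclear, not explicit. It does not dispose of the point. The response-point version recovers almost nothing, and change scores lose precision unless the pre/post correlation exceeds 0.5.

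Three stronger readings are tempting, and the documents do not support them.
- A reader might infer that the contrasts are biased. Order is randomized, so a chance difference in pre-dose severity between days is sampling error.
- A reader might infer that adjustment removes the day effect or makes the tests valid. It does neither by itself. The near-5% error rates belong to a session-level analysis, which is not the planned model.
- A reader might infer a known, large loss. With no variances stated, the result runs from a slight cost to a large gain. For a single reading, break-even is at a within-person pre/post correlation of about 0.19, and at 0.3 the variance saving is only about 5%.

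It is also fair to say that baseline adjustment in a crossover is a refinement, and that it cannot apply to the MRF.

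**Conclusion.** The point holds as a matter of efficiency and clarity. The plan does not state the role of the -30 minute score and lists no term for it, so day-to-day variation stays in the level contrasts. Under the assumed participant share of 0.5, adjustment moves the SE by between +2% and -31% as session share goes from 0 to 0.3. The direction is favourable unless sessions hardly differ. The figures assume 15 complete participants, equal variances and no carryover.

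The change is worth making, but only together with a session random effect. Without it the narrower contrast would still be tested against an SE that is too small whenever sessions differ.

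**What to change.** In the Cannabis Effects paragraph, for YBOCCS, OCD-VAS, STAI-S and the cardiovascular measures:

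1. State that the outcomes are the six post-dose readings.
2. Add two covariates: the session's -30 minute score as a deviation from the participant's mean of the available -30 minute scores, and that mean. Using the available scores covers participants who miss a session; the continuation report already records 2 discontinuations among 5 enrolled.
3. Add a participant-by-session random intercept and name a small-sample degrees-of-freedom method.
4. Report the contrasts without the pre-dose covariates, from the otherwise identical model, as a sensitivity analysis.
5. Leave the MRF unadjusted, since it has no pre-dose reading, but give it the session term.

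The cost is a few sentences and no new data or visits. Intervals are about 2% wider if sessions do not differ. If residual drug from an earlier session moves the -30 minute score, the adjustment passes part of that into the contrast; comparison with the unadjusted result would help to show it. The change should be fixed before any results by condition are seen.

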Subjects may be receiving either psychotherapy or medication management in the community while they participate in this study; however, they will not be eligible for participation in this study if they a) are taking a selective SRI or clomipramine and have altered their dose in the 6 weeks prior to study enrollment or are planning to make changes to their medications during the period of the study (approximately 3 weeks), b) are taking psychotropic medications other than selective SRIs or clomipramine, or c) have begun cognitive-behavioral therapy within 8 weeks prior to enrollment or plan to commence cognitive-behavioral therapy during the period of the study (approximately 3 weeks). For subjects who are not currently receiving any treatment for OCD and are interested, referrals for external treatment providers will be given.”

Eligible subjects who have finished other studies in the Anxiety Disorders Clinic will be offered participation if they are eligible. These protocols will include:

IRB#6628 Attaining and maintaining wellness in OCD

IRB#7000 Control and Reward Circuits in OCD

IRB#7127 Toward Precision Medicine for OCD

IRB#7059 Pilot study of personalized-computerized inhibitory control training for OCD

IRB#6837 Internet Based Treatment for OCD (iCBT)

IRB#7239 Cannabinoid Medication for Adults with OCD

IRB#7572 Feasibility, Acceptability and Preliminary Efficacy of a Mobile App (nOCD) for OCD

Inclusion/Exclusion Criteria

Name the subject group/sub sample

Adults with OCD

Create or insert table to describe the inclusion criteria and methods to ascertain them

- 1. Patient must be 21-55 years of age at the time of consent
Clinical interview
- 2. Patient must be physically healthy male or non-pregnant female. Females of childbearing potential must comply with contraceptive restrictions noted in the protocol.
Clinical interview by trained M.D. or Ph.D., physical examination by M.D., ECG, and blood tests
- 3. Patients must fulfill DSM 5 criteria for OCD, OCD being the principal disorder (i.e., currently the most severe and needing of treatment), and have had OCD for at least one year with near-constant symptoms.
Clinical Interview by trained M.D. or Ph.D. and results of SCID
- 4. Patients with a Y-BOCS score of greater than or equal to 16 prior to entering trial.
Clinical interview and assessment by trained rater
- 5. Patient has smoked marijuana at least once in the past and did not experience intolerable side effects.
Clinical Interview

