** BP/HR = blood pressure and heart rate; VAS = Visual Analogue Scale; YBOCCS = Yale-Brown Obsessive-Compulsive Challenge Scale; MRF = Marijuana Rating Form; STAI = State/Trait Anxiety Inventory; TLFB = Marijuana Timeline Followback

Patients will be required to take public transportation to and from the laboratory each session, for which they will be reimbursed. Study clinicians will conduct the Field Sobriety Test. After confirming that the participant has passed the Field Sobriety Test, the patient will be allowed to leave the laboratory. If a participant is still impaired at the end of the session, she or he will be asked to remain in the laboratory until the effects wear off, and will be paid extra (i.e. \$10 per hour for any additional time in the laboratory). In the event that the impairment does not resolve in a timely manner, a study physician will determine whether the person can leave the laboratory or if further action is needed. It is worth noting that in our experience, it is exceedingly rare (<1% of all participants) for marijuana smokers to remain intoxicated several hours after smoking marijuana in the laboratory.

Laboratory Facility: Experimental sessions will be conducted in the Substance Use Research Center (SURC) located on the 3rd floor of the NYS Psychiatric Institute.

Safety Measures: Vital signs (heart rate and blood pressure) will be monitored in each session. If SBP > 180 mmHg, DP > 110 mmHg, or HR > 120 bpm, these measures will be taken 2 additional times at 2 min intervals: A physician will see the participant immediately if blood pressure or heart rate remain above these levels for 3 continuous readings.

Data Analysis: A between and within-subject repeated measures analysis of variance (ANOVA) with planned comparisons will be implemented to determine the effects of marijuana on OCD symptoms

You can upload charts or diagrams if any

Criteria for Early Discontinuation

Criteria for Early Discontinuation

Participants are free to withdraw from the study at any time for any reason. Study doctors are to discontinue patients from the study if patients:

- Request an early discontinuation or withdraw consent.
- Experience a serious or intolerable adverse event that prevents the patient from continuing.

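### The active-placebo contrasts compare sessions, but the model has no session term and no planned use of each session's pre-dose reading

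*Combined protocol and SAP*

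**What the plan says.** The Data Analytic Plan, under Cannabis Effects, lists the model terms as participants as a random effect, "condition and time as fixed within-subjects factors, the interaction between condition and time, and a random intercept". It adds that "we will model time as a continuous variable", and justifies the approach because "Mixed-effects modeling accounts for clustering of repeated measures within subjects". The results of interest are contrasts that "estimate differences in outcomes between both active cannabis varieties and placebo at different time points". The only covariates named are age, gender, comorbid diagnoses and other unspecified factors, in separate exploratory analyses.

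Table 1 (Session Schedule) has this entry at -30 minutes in every session: "balance, TLFB, BP/HR, VAS, YBOCCS, STAI". Six post-dose readings follow, at 20, 40, 60, 90, 120 and 180 minutes. The MRF starts only at 20 minutes.

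The Data Analysis sentence in Study Procedures names a different method, "A between and within-subject repeated measures analysis of variance (ANOVA) with planned comparisons". Neither text says whether the -30 minute reading is a response, a covariate or unused.

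**The concern.** Each participant has three sessions, one per condition. An active-placebo difference at a time point is therefore a difference between two mornings in the same person. A bad night, a stressful day or the participant's own marijuana use (barred only from midnight before a session) can move all readings of one morning together. The participant intercept cannot absorb that shift. It treats the six post-dose readings of a session as independent given the participant, so the model reports more information than the data hold.

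Two things follow. The reported SE is too small, so p-values are too small. And the contrast is noisier than necessary, because the pre-dose reading that measures part of the shift has no stated use.

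The study hypothesis is that both active types "will lead to a reduction in symptoms in adults with primary OCD who are also occasional marijuana smokers as compared to placebo". In 15 completers, a false-positive rate several times the nominal level would make a positive contrast hard to interpret.

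**Working it through.** The documents give no effect size, SD or power, so the 15 completers cannot be reproduced. The check concerns the error of the contrast when there is no drug effect.

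**Inputs.** From the documents: 15 completers, 3 sessions each, the Table 1 reading times, linear time, two-sided alpha 0.05. Assumed: within-participant variance 1, split into a session shift with variance r and independent noise with variance 1 - r. The value of r is not given, so 0 to 0.7 is shown.

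**True SE at 60 minutes, post-dose readings only.** The six times have mean 85 and sum of squared deviations 17,150. A fitted line at 60 minutes carries noise factor g = 1/6 + 25²/17,150 = 0.203. One session's fitted value has variance v = r + 0.203(1 - r), and the contrast has SE = √(2v/15).

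**SE the planned model reports.** There are 15 × 3 × 6 = 270 readings and 20 mean parameters (15 participant, 2 condition, 1 time, 2 interaction), leaving 250 residual df. Session shifts have 45 - 15 - 2 = 28 df, each carrying 6r. The expected residual variance is s² = (1 - r) + 28 × 6r/250, and the reported SE is √(2 × s² × 0.203/15).

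**False-positive rate.** This is approximately 2[1 - Φ(2.056 × reported SE / true SE)], where 2.056 is the t(26) critical value.

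| r | v | true SE | s² | reported SE | false positives, formula | false positives, simulation |
|---|---|---|---|---|---|---|
| 0.1 | 0.283 | 0.194 | 0.967 | 0.162 | 8.7% | 8.9% |
| 0.3 | 0.442 | 0.243 | 0.902 | 0.156 | 18.6% | 18.9% |
| 0.5 | 0.602 | 0.283 | 0.836 | 0.150 | 27.5% | 28.0% |
| 0.7 | 0.761 | 0.319 | 0.770 | 0.144 | 35.1% | 36.2% |

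The simulation fitted the mixed model by REML in 2,000-2,500 runs. A separate simulation with residual df in place of t(26) gave 10%, 22%, 30% and 39%. With the -30 minute reading kept as an ordinary time point, it gave 12%, 27%, 37% and 47%.

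**Other time points.** For the planned model at r = 0.3, 0.5 and 0.7, the rates are 10%, 15% and 21% at 20 minutes, and 7%, 9% and 12% at 180 minutes. Sixty minutes lies near the centre of the time scale, where inflation is close to its largest.

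**Effect of the covariate on the true SE.** The ratio to the post-dose-only planned model is √[(1 - r²/v) × 27/26]:

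- r = 0.3: √[(1 - 0.09/0.442) × 1.038] = 0.91
- r = 0.5: √[(1 - 0.25/0.602) × 1.038] = 0.78
- r = 0.7: √[(1 - 0.49/0.761) × 1.038] = 0.61

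Simulated SEs fall from 0.244, 0.285 and 0.320 to 0.219, 0.219 and 0.193, gains of 10%, 23% and 40%. If the shift fades over the session (correlation decaying as exp(-minutes/240)), the gains are 5%, 11% and 19%. At r = 0.5, that range is worth 15/0.887² = 19 to 15/0.77² = 25 completers. At r = 0 the covariate loses 1-2%; at 0.1 it changes nothing.

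**What restores the error rate.** At r = 0.1, 0.3, 0.5 and 0.7, the covariate alone leaves 8%, 15%, 20% and 24%. The covariate with a participant-by-session intercept gives 4.3%, 4.7%, 4.9% and 5.2%. A session-level error term without the covariate gives 4.5-5.6% over r = 0 to 0.7.

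**If -30 minutes is a response on the line.** Take a constant effect of 1 from 20 to 180 minutes and 0 at -30. The seven times have mean 68.6 and sum of squared deviations 28,486; the fitted slope is 98.57/28,486 = 0.00346 around a mean of 6/7. The effect is then fitted as 0.69 at 20 minutes, 0.83 at 60 and 1.24 at 180.

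**The case against.** The strongest reply is that the finding joins two different points. Order is randomised, so chance differences in starting symptoms cause no systematic bias. The session term alone repairs the error rate, and the covariate only adds precision. That is correct, and the two parts should be weighed separately.

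Second, the inflation is not general. The condition-by-time slope is safe against an additive shift: its simulated error rate, with the -30 minute reading included, is 5.2%, 2.9% and 1.2% at r = 0, 0.3 and 0.5. A standard repeated-measures ANOVA tests condition against participant-by-condition error, which here is session-level error, and holds about 5%. This stands, but the more detailed Data Analytic Plan specifies time-point contrasts from a model without that error term. Its reference to changes in outcomes does not define a change score either. Without a session term, change from the pre-dose reading would still give about 28-31%.

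Third, r is assumed. Participants must "have had OCD for at least one year with near-constant symptoms" and be on stable medication or none, which may keep shifts small. This also stands. Yet at r = 0.1 the error rate is already near 9%.

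Fourth, the covariate is not free on every reading of the plan. If -30 minutes would otherwise be a response, moving it to a covariate raises the true 60-minute SE by 19% at r = 0 and 9% at 0.1. The two are equal near 0.2, and the SE is 6%, 21% and 39% lower at 0.3, 0.5 and 0.7. With a fading shift it is 4% higher at 0.3, and 5% and 14% lower at 0.5 and 0.7. Finally, the calculations assume 15 complete participants, and two of the first five withdrew.

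**Conclusion.** The concern holds. As written, the time-point contrasts are between-session comparisons without session-level error, and the pre-dose reading has no stated role. The 60-minute false-positive rate is about 9% to 36% for r from 0.1 to 0.7, with smaller inflation at 20 and 180 minutes and none at r = 0.

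The missing session term is an error in the analysis whenever days differ. The covariate is a worthwhile gain when r is about 0.2 or more. The sizes rest on the assumed r, a linear time course, complete data and tests on t(26). With a fading shift, the fix gains at most 3% at 180 minutes and leaves 5-8% false positives there. The sponsor should make the change; confidence in the size is medium because r is unknown.

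**What to change.** In the Data Analytic Plan, under Cannabis Effects, before unblinding:

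1. Model only the 20-180 minute readings as responses.
2. Add a participant-by-session random intercept for every outcome, and state the degrees-of-freedom method. The calculations here used t(26); a normal cut-off gives about 6%.
3. For YBOCCS, OCD-VAS, STAI-S and the cardiovascular measures, add the same session's -30 minute reading as its deviation from the participant's mean -30 minute reading, with that mean as a second term. Centring matters: with a session intercept and participant variance 3, an uncentred covariate raised the SE by 12% at r = 0.3.
4. Analyse the MRF without the covariate, since it has no pre-dose reading.

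This takes two or three sentences and no new data. The covariate uses one within-participant degree of freedom per outcome (28 to 27 at session level). Reported intervals become wider but honest: at r = 0.5 the reported 60-minute SE rises from 0.150 to 0.216, against a true SE of 0.219 after the fix. The main price is the loss of precision at r of 0.1 or less if -30 minutes would otherwise have been a response.
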